6.0 Data Banking

6.1 Storage and Access:

All data will be stored in HIPAA compliant systems, including encrypted University storage systems requiring dual-factor authentication and only accessible to members of the research team. All research team members with access to data will have human subjects research (CITI training) and HIPAA training.

6.2 Data:

Data elements to be collected are included in the table below:

Construct	Measure	Time administered
Surveys (providers)		
Demographics	Age, gender, race/ethnicity, discipline, years of experience, etc.	Post training, post pilot year
Acceptability	Acceptability of Intervention Measure (4 items)	Post training, post pilot year
Acceptability	Readiness to Change Assessment, patient preferences	Post training, post pilot

SOCIAL PROTOCOL (HRP-580)

PROTOCOL TITLE:

VERSION DATE:

	(4 items)	year
Appropriateness	Intervention Appropriateness Measure (4 items)95	Post training, post pilot year
Feasibility	Feasibility of Intervention Measure (4 items)95	Post training, post pilot year
Communication Skills	Vignettes (5 items), coded with adapted GenPMTO fidelity manual	Post training, post pilot year
Referral counts (HCMC)		
Referral counts	Rates of referral and total number of children ages 3-5 seen by provider	Post pilot year
Focus Group (providers)		
Demographics (aggregate)	Age, gender, race/ethnicity, discipline, years of experience, etc.	Post pilot year
Acceptability, Appropriateness, Feasibility	Transcript	Post pilot year

6.3 Release/Sharing:

Prior to release, all data will be de-identified so that it cannot be linked back to individuals, following IRB-approved protocols for de-identification. All de-identified quantitative data will be shared with the NIMH Data Archive (NDA) following study completion. The quantitative data we make available will be cleaned and coded and will be accompanied by a data dictionary that documents the (a) response/coding definitions, (b) missing value definitions, (3) any skip patterns, and (4) reference for the origin of each measure. Qualitative data will be shared to the extent that it is feasibly de-identified when requested by outside researchers.

7.0 Sharing of Results with Participants

No individual participant results will be shared with participants or others.

An overview of the results of the survey will be presented to focus group participants to solicit their reflections and further insights.

8.0 Study Duration

8.1 A study timeline is provided below.

	2021	2022	2022	2022	2022	2023	2023	2023	2023	2024	2024
	Sep - Nov	Dec - Feb	Mar - May	Jun - Aug	Sep - Nov	Dec - Feb	Mar - May	Jun - Aug	Sep - Nov	Dec - Feb	Mar - May
Recruit PC personnel in two collaborating clinics											
Deliver training to PC personnel randomized to the training condition											

SOCIAL PROTOCOL (HRP-580)

PROTOCOL TITLE:

VERSION DATE:

Conduct post-training survey with PC personnel							
Preliminary analysis of post-training survey data							
Year-long pilot							
Conduct post-pilot survey with PC personnel							
Analysis of survey data							
PC personnel focus groups, based on survey results							
Analysis of focus group and interview data							
Analysis of referral and engagement rates between training & control PC personnel							

Provider participants are anticipated to participate in the survey for about fifteen months, beginning with the training or written description of referral process, participation in the survey and year-long pilot, final survey, and concluding with a focus group. We estimate it will take four months to recruit all providers.

Some data analysis will be completed concurrent with study procedures, and we estimate an additional six months of data analysis will be required following completion of all participant study procedures.

9.0 Study Population

9.1 Inclusion Criteria:

Inclusion criteria for providers include being an advanced practice provider (Physician, Resident, or RN) currently seeing clients at Hennepin Healthcare clinics, being willing to participate in the research, and be willing to participate in a referral training.

Vulnerable populations will not be targeted for inclusion, although they will be included if they are advanced practice providers who meet the other inclusion criteria.

9.2 Exclusion Criteria:

There are no known criteria that would exclude participants from the final sample.

9.3 Screening:

Providers interested in participating will contact the research team. The research team will review the study procedures and eligibility criteria.

10.0 Vulnerable Populations

10.1 Vulnerable Populations:

Population / Group	Identify whether any of the following populations will be targeted, included
--------------------	------------------------------------------------------------------------------

SOCIAL PROTOCOL (HRP-580)**PROTOCOL TITLE:****VERSION DATE:**

	(not necessarily targeted) or excluded from participation in the study.
Children	Excluded
Pregnant women/fetuses/neonates	Included
Prisoners	Excluded
Adults lacking capacity to consent and/or adults with diminished capacity to consent, including, but not limited to, those with acute medical conditions, psychiatric disorders, neurologic disorders, developmental disorders, and behavioral disorders	Excluded
Non-English speakers	Included
Those unable to read (illiterate)	Excluded
Employees of the researcher	Excluded
Students of the researcher	NA
Undervalued or disenfranchised social group	Included
Active members of the military (service members), DoD personnel (including civilian employees)	Included
Individual or group that is approached for participation in research during a stressful situation such as emergency room setting, childbirth (labor), etc.	NA
Individual or group that is disadvantaged in the distribution of social goods and services such as income, housing, or healthcare.	Included

SOCIAL PROTOCOL (HRP-580)**PROTOCOL TITLE:****VERSION DATE:**

Individual or group with a serious health condition for which there are no satisfactory standard treatments.	NA
Individual or group with a fear of negative consequences for not participating in the research (e.g. institutionalization, deportation, disclosure of stigmatizing behavior).	NA
Any other circumstance/dynamic that could increase vulnerability to coercion or exploitation that might influence consent to research or decision to continue in research.	NA

10.2 Additional Safeguards:

The purpose of this study is to test the referral process to address barriers to access in the general population, including groups disadvantaged in the distribution of social goods and services, who speak different languages, and are from disenfranchised groups. Primary care clinics reach a large portion of the population, including low-income individuals, underinsured individuals, and individuals speaking multiple languages.

There is a significant need to increase access to effective preventive services among families who would benefit^{12,13}. Including these populations in our study is necessary to test whether this referral process facilitates access. The population impact of these programs on children's behavioral health is a function of the effectiveness of the programs and the number of parents/families that participate. This research will contribute to a growing effort to integrate these programs into primary care settings, which is widely accessible and non-stigmatizing. The knowledge gained from this study is a step toward the effective integration of evidence-based prevention programs, which will potentially benefit the families involved in the research and will certainly benefit members of their communities.

The risks of this study are minimal, and the risks or discomforts should not be greater for vulnerable populations than for other populations.

11.0 Number of Participants**11.1 Number of Participants to be Consented:**

We plan to enroll 35 medical providers who work with children between three-five years old at the two clinics. Half of the participants will be randomly assigned to each study arm; n=15 of the 35 will be recruited for focus groups.

SOCIAL PROTOCOL (HRP-580)

PROTOCOL TITLE:

VERSION DATE:

This pilot study is not meant to provide conclusive fully-powered effectiveness results. These analyses will be useful in guiding focus group topics, and generating effect size estimates and variance components to guide proceeding with an R01 application for a fully-powered randomized trial.

12.0 Recruitment Methods

12.1 Recruitment Process:

Two partners at HCMC, Drs. [name] and [name], will share information by email to recruit providers.

12.2 Source of Participants:

Providers will be drawn from Hennepin Healthcare clinics.

12.3 Identification of Potential Participants:

Provider participants will then self-identify in response to email contacts by Drs. [name] and [name] at HCMC.

12.4 Recruitment Materials:

Providers will be recruited by sharing a flyer by email from Drs. [name] and [name]. A copy of the “Provider recruiting and expectations” flyer is attached.

12.5 Payment:

Provider incentives for surveys and focus groups. Providers will receive a \$50 gift card for survey completion at each time point (after the training and after the pilot year). A subset of providers will receive a \$100 gift card for focus group participation. The maximum amount of incentives would be \$200. Gift cards will be sent electronically using tango.com within a week following survey completion or focus group participation.

13.0 Withdrawal of Participants

13.1 Withdrawal Circumstances:

There are no specific foreseeable events that would preclude primary care personnel from participating.

13.2 Withdrawal Procedures:

If a participant chooses to withdraw, they will contact the therapist or research team, so the research team can remove their name from the list of participants to send a follow-up survey or focus group invitation. Data that was collected prior to withdrawal will be included in the database, unless the participant requests for it to be deleted.

13.3 Termination Procedures:

SOCIAL PROTOCOL (HRP-580)

PROTOCOL TITLE:

VERSION DATE:

We do not believe there is any reason the study would be terminated. If it were unexpectedly suspended or terminated, the researchers would notify all participants of the suspension or termination, as well as a plan for participating therapists to address any outstanding reimbursements. The research team would notify the IRB with the reason for the suspension or termination, enrollment update, and the plan for notifying participants. Data collected prior to termination would be used to assess feasibility of future research.

14.0 Risks to Participants

14.1 Foreseeable Risks:

The primary potential risk is a breach of confidentiality. Given the nature of this study, this risk is minimal. There is also a small risk of frustration, stress, or sense of added burden by study activities. Nevertheless, every possible precaution will be taken to protect against these risks, as described below.

Informed Consent and Assent (Protection against coercive recruitment)

All participants in data collection will be given a consent form that highlights the voluntary nature of data-collection activities. Providers are free to participate in the research or not, without ramifications on future opportunities with the University of Minnesota. The value of the gift cards given to participants is consistent with the PI's previous research and is not likely to be viewed as or function as coercive recruitment.

Protections Against Risks

To protect against breach of confidentiality, any raw and digital data will be closely protected by the study team. Electronic data will be transferred via encrypted hard drives and uploaded to a secure University of Minnesota server. Data will be de-identified and a document linking the participant names and random ID numbers will be encrypted and stored on a separate secure folder only accessible by the PI and the project manager. All team members with access to the de-identified data will be added to the IRB approval for the study and will have completed the Collaborative Institutional Training Initiative (CITI) ethics training and HIPAA training required by the University of Minnesota. Findings from these data that are published or given to participating clinics will be sufficiently aggregated and de-identified so that no reader would be able to identify individual quotes or data.

Participants will be told that their names will not be attached to any of their answers and that nobody will ever know what they say in interviews. They will be told that the sole exception to this is if we were to learn about child abuse or imminent danger to self or another.

Participants in focus groups will be reminded of confidentiality and instructed that this also pertains to sharing about the group discussions and other participants. They will be instructed to not share what was discussed or who was at the group.

Providers will be instructed that feedback about any burdens or stress caused by the program are welcome and, in fact, provide valuable insight into the practicality and scalability of the model. We will ensure they have contact information for multiple study team members to share any concerns. Any concerns that are raised will be discussed among the research team members and will be addressed on a case-by-case basis.

Response to adverse events

Instances of abuse, suicidality, or imminent harm may be identified, although this is unlikely. This study does not specifically address abuse nor are there questions that would likely illicit this information. All therapists trained in this study to provide GenerationPMTO are licensed mental health professionals and are equipped to take appropriate actions if they learn about abuse or neglect. They will also be given the contact information for [name] to consult if a situation arises. They will be informed of the need to report the event to [name] as soon as possible.

SOCIAL PROTOCOL (HRP-580)

PROTOCOL TITLE:

VERSION DATE:

14.2 Reproduction Risks: NA

14.3 Risks to Others: NA

15.0 Incomplete Disclosure or Deception

15.1 Incomplete Disclosure or Deception: NA

16.0 Potential Benefits to Participants

16.1 Potential Benefits:

Providers will receive a referral list that may be a useful tool in serving families of children with behavior challenges and reduce provider load. Half will receive communication skills training that may increase their skills in communicating with and motivating parents.

17.0 Statistical Considerations

17.1 Data Analysis Plan:

In order to measure communication skills, we will code the audiorecorded responses to vignettes. Because the communication skills in the PC training will mirror the therapist skills in GenPMTO, we will adapt relevant components of the Fidelity of Implementation Rating System⁴¹ and two coders will rate the quality of response, accounting for confronting, teaching, supporting, and facilitating.

We will examine the preliminary effectiveness of the PC personnel training. We hypothesize that communication skills and referral rates, will both be higher in the training group compared to the control group. While this pilot study *is not meant to provide sufficient power for significance testing*, these hypotheses will guide our analyses. We will analyze differences between training and control groups on outcomes including communication skill and referral rates, using generalized linear multivariate regression. We will examine communication skill items individually and assess the psychometrics of the items as a scale and as indicators of a latent variable. Each outcome will be analyzed in a separate model. In the first analysis, we will only enter training condition as a dummy variable (i.e., t-test) to examine between group differences. In subsequent analyses we will include covariates to account for clinical experience and demographic variables. Primary covariates include discipline (i.e., family medicine or pediatrics department) and years of experience. We will also examine differences by clinic location and examine intra-class correlations. These analyses will be useful in guiding focus group topics, examining the usefulness of the survey items we adapt and create, and generating effect size estimates and variance components for a fully-powered trial. Finally, we will examine the indirect effect of the PC personnel training on parent engagement through the mechanism (mediation) of PC personnel communication skills. For mediation analyses, we will use path models in MPlus with bootstrapped indirect effects.

As benchmarks for comparison, other studies that have targeted referral practices and behaviors have found medium-sized effects (e.g., $d=.50-.66$) on some PC practice outcomes. In these same studies, researchers reported attrition ranging from 0-15%.³⁴⁻³⁵ These estimates correspond with minimum sample sizes ranging from 76-148 to achieve power of .80 to detect a difference between the study arms. Our sample size of 35 results in power of .47 to detect an effect of .66, or power of .61 with a one-tailed test. These power analyses illustrate why this study is needed in preparation for an R01. The effect size estimates we produce in this study and the attrition that we observe will allow us to determine if the effect of the PC personnel training is in the same range as effects seen in other studies. These estimates will inform the sample size we

SOCIAL PROTOCOL (HRP-580)**PROTOCOL TITLE:****VERSION DATE:**

propose in a subsequent R01 application; without the estimates from the present study we may significantly over or under estimate the sample size needed.

Based on the estimates we generate from the current study, we will run Monte Carlo simulations in MPlus to determine reasonable sample sizes for our R01 application. We will conduct these simulations to determine optimal sample sizes and allocation ratios between study arms. In addition, using the estimates of effect sizes, variance components, and attrition, we will model various analytic strategies and measurement approaches. We will conduct these advanced simulations with support and consultation of the college's Research Methodology Consulting Center.

17.2 Power Analysis:

NA

17.3 Statistical Analysis:

See section 17.1

17.4 Data Integrity:

The PI, in collaboration with the data safety monitoring committee, will monitor the data integrity. In weekly meetings with the project manager, the PI will review the data collected that week, that random assignment with blinding is carried out appropriately, and that data is being collected securely and in accordance with best practices. A brief report of the data integrity will be included in twice annual updates to the data safety monitoring committee.

18.0 Health Information and Privacy Compliance**18.1 Select which of the following is applicable to your research:**

My research does not require access to individual health information and therefore assert HIPAA does not apply.

I am requesting that all research participants sign a HIPCO approved HIPAA Disclosure Authorization to participate in the research (either the standalone form or the combined consent and HIPAA Authorization).

I am requesting the IRB to approve a Waiver or an alteration of research participant authorization to participate in the research.

Appropriate Use for Research:

An external IRB (e.g. Advarra) is reviewing and we are requesting use of the authorization language embedded in the template consent form in lieu of the U of M stand-alone HIPAA Authorization. Note: External IRB must be serving as the privacy board for this option.

SOCIAL PROTOCOL (HRP-580)

PROTOCOL TITLE:

VERSION DATE:

18.2 Identify the source of Private Health Information you will be using for your research (Check all that apply)

NA

- I will use the Informatics Consulting Services (ICS) available through CTSI (also referred to as the University's Information Exchange (IE) or data shelter) to pull records for me
- I will collect information directly from research participants.
- I will use University services to access and retrieve records from the Bone Marrow Transplant (BMPT) database, also known as the HSCT (Hematopoietic Stem Cell Transplant) database.
- I will pull records directly from EPIC.
- I will retrieve record directly from axiUm / MiPACS
- I will receive data from the Center for Medicare/Medicaid Services
- I will receive a limited data set from another institution
- Other. Describe:

18.3 Explain how you will ensure that only records of patients who have agreed to have their information used for research will be reviewed.

NA

18.4 Approximate number of records required for review:

NA

18.5 Please describe how you will communicate with research participants during the course of this research. Check all applicable boxes

- This research involves record review only. There will be no communication with research participants.
- Communication with research participants will take place in the course of treatment, through MyChart, or other similar forms of communication used with patients receiving treatment.
- Communication with research participants will take place outside of treatment settings. If this box is selected, please describe the type of communication and how it will be received by participants.

Interview invitations will be sent by email or text, depending on participant preference.

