3.0 Study Endpoints/Events/Outcomes

3.1 Primary Endpoint/Event/Outcome:

SOCIAL PROTOCOL (HRP-580)

PROTOCOL TITLE:

VERSION DATE:

The primary study outcome is referral rates. Note that parent engagement will also be measured in a separate arm of the study, captured in a separate IRB protocol.

We will also assess acceptability, feasibility, and appropriateness of the training and referral process to PC personnel. Note that the acceptability of the referral process among parents will also be measured in a separate arm of the study, captured in a separate IRB.

3.2 Secondary Endpoint(s)/Event(s)/Outcome(s):

The secondary outcome is PC personnel communication skills.

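### Section 17.1 says the 35-provider pilot will determine whether the training effect matches other studies; with 35 providers the estimate is too imprecise to do that (wrong as written).

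*Combined protocol and SAP*

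**What the plan says.** The power paragraph of Section 17.1 cites d = .50 to .66, with attrition of 0 to 15%, from studies that targeted referral practices. It gives the sample sizes those figures imply for a powered trial ("These estimates correspond with minimum sample sizes ranging from 76-148 to achieve power of .80"). For this pilot it gives power of .47 at d = .66, or .61 one-tailed.

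It then says the pilot's effect size estimates and observed attrition "will allow us to determine if the effect of the PC personnel training is in the same range as effects seen in other studies". The pilot is justified on the ground that "without the estimates from the present study we may significantly over or under estimate the sample size needed". The next step is also tied to the estimates: "Based on the estimates we generate from the current study, we will run Monte Carlo simulations in MPlus to determine reasonable sample sizes".

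Two caveats appear elsewhere. Section 11.1 says "This pilot study is not meant to provide conclusive fully-powered effectiveness results", and earlier in Section 17.1 the pilot "is not meant to provide sufficient power for significance testing". No confidence interval or other measure of precision for d is given. The only interval-type method named is bootstrapping of the indirect effects in the mediation model.

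Section 3.1 states "The primary study outcome is referral rates"; communication skill is the secondary outcome (Section 3.2).

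**The concern.** The effect estimate is one of the pilot's main declared products, so its precision is what a reader most needs. The plan discloses low power for testing, but then makes a separate claim about estimation: that the estimate will settle whether the effect lies in a particular narrow range. A study too small to test the effect can still give a useful estimate, provided the uncertainty is reported and carried forward. It cannot place the true effect inside or outside a band 0.16 wide.

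Two things are at stake. An estimate near .50 to .66 could be reported as agreeing with other studies when the same data fit no effect or a much larger one; an estimate outside the band could be reported as disagreeing when the true effect lies within it. And if the R01 simulations were run only at the pilot's point estimate, they would be exposed to the sample-size error that the pilot is meant to prevent.

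**Working it through.** **Inputs.** Total N = 35, half to each arm (Section 11.1), taken as 17 and 18. Benchmarks d = .50 to .66 and attrition 0 to 15% (Section 17.1). The first analysis is an unadjusted two-group comparison, equivalent to a t-test (Section 17.1). Alpha is not stated; two-sided .05 is assumed, and it reproduces the plan's power.

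**Step 1: the plan's own figures.** Let s = sqrt(1/17 + 1/18) = 0.338 and df = 33. At d = .66 the noncentrality is .66/0.338 = 1.95. Noncentral-t power is .474 two-sided and .605 one-sided, matching .47 and .61. For power .80 the t-test needs a total of 76 at d = .66. At d = .50 the normal approximation gives 126, and 126/.85 = 148.2, which is consistent with the upper figure of 148 including 15% attrition. The model used below is therefore the plan's own.

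**Step 2: confidence interval for d.** Set t = d/s, find the noncentrality values that put t at the 2.5% and 97.5% points of the noncentral t distribution, and multiply each by s.

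| Analysed | Observed d | 95% interval | Width |
|---|---|---|---|
| 17/18 | .50 | -0.18 to 1.17 | 1.35 |
| 17/18 | .58 | -0.10 to 1.25 | 1.35 |
| 17/18 | .66 | -0.03 to 1.34 | 1.36 |
| 15/15 | .50 | -0.23 to 1.22 | 1.45 |
| 15/15 | .66 | -0.08 to 1.39 | 1.47 |

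Widths are taken from the unrounded limits. The 15/15 rows lose 5 of 35 (14%), inside the cited attrition range. The benchmark range is .66 - .50 = 0.16 wide, so the 17/18 interval is about 1.35/0.16 = 8 times as wide.

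Zero is excluded at 95% only when observed d reaches t(.975, 33) × s = 2.035 × 0.338 = 0.69, above the top benchmark. With 15/15 the threshold is 0.75.

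**Step 3: how often the estimate would fall in the range.** With 17/18, P(.50 < observed d < .66) = F(.66/s) - F(.50/s), where F is the noncentral t distribution function with df 33 and noncentrality (true d)/s.

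| True d | Probability |
|---|---|
| 0 | .045 |
| .20 | .099 |
| .50 | .176 |
| .58 | .182 |
| .66 | .177 |
| 1.00 | .089 |

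An effect in the middle of the range gives an estimate outside it about 82% of the time. An estimate inside the range is only about twice as likely under a true d of .58 as under .20 (.182/.099 = 1.8) or 1.00 (.182/.089 = 2.0).

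**Step 4: what follows for the R01 simulations.** Take an observed d of .66 with 17/18. The 80% interval by the Step 2 method is 0.21 to 1.10. Total N for power .80 (two-sided .05, 1:1, before attrition) is 76 at the estimate, 28 at the upper limit and 718, or about 720, at the lower limit.

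**The case against.** The strongest reply is that this is a pilot and says so. It disclaims conclusive results and significance testing and prints its power of .47. A 95% interval that includes 0 at an observed .66 carries much the same message as that power. On this view the point rests on one verb, which might be read as meaning a descriptive comparison. Much of this stands: low power is disclosed, and the inclusion of zero is not the new information. At .66 with 17/18 it is also a narrow matter (-0.03). What remains is the width of the interval and the 18% figure. The caveats concern effectiveness results and testing; neither qualifies the statement about locating the effect among other studies.

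Second, stating no interval is not the same as planning to omit one. Regression models yield standard errors, and the simulations are to explore several strategies with methodological consultation. That is fair. A reader might infer that the plan commits to reporting d without uncertainty, or to sizing the R01 at the point estimate. The documents say neither; they are silent on whether the uncertainty is carried forward.

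Third, a reader might infer from Step 4 that the pilot tells us less than the published studies behind the 76 to 148 range. That does not follow. Those totals come from published point estimates, with the upper one apparently inflated for attrition, while Step 4 uses confidence limits before attrition. The precision of the published effects is not given.

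Fourth, the intervals are for d, whereas the primary outcome is a referral rate built from provider counts and numbers of children seen (Section 5.2). This stands as a limit on the figures.

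**Conclusion.** The statement is wrong as written. For an approximately normal outcome, 35 providers cannot determine whether the effect lies in the range of other studies: the 95% interval is about 1.35 wide against a range of 0.16, and a true effect of .58 would produce an estimate inside the range only about 18% of the time.

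This rests on two-sided alpha of .05, a 17/18 split, independent providers and an unadjusted d. Attrition within the cited range widens the interval. For referral rates the d figures are only approximate, and no precision on a rate scale has been computed here.

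The conclusion should not be stretched. A reader might infer that the power calculation is wrong or that the sample is too small for a pilot; the power figures reproduce, and the documents present the study openly as underpowered preparation for a larger trial. A reader might also take the line "We will also examine differences by clinic location and examine intra-class correlations" as a plan to estimate a clinic-level correlation from two clinics. The text does not name the level, and Section 26.1 allows recruitment from further clinics, so that is not part of this point.

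**What to change.** In Section 17.1, replace the sentence claiming to determine agreement with other studies by something like: *We will report the effect estimate for each outcome with its confidence interval (d for the skills score, a rate ratio or rate difference for referrals) and compare it descriptively with published benchmarks. The pilot is not expected to distinguish a benchmark-sized effect from no effect or from a much larger one.*

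In the simulation paragraph, state that the R01 Monte Carlo runs will cover the pilot's confidence interval and the published range of effects, rather than the pilot point estimate alone.

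The cost is a change of wording, a few interval calculations and some extra simulation settings. The stated precision will look less favourable. No participants, procedures or data are added.
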